6.4.2. BLRM analyses for Dose-limiting toxicity (Substudies 3 and 5 only)

Safety interim analyses will be performed once 10 patients have been enrolled and full safety data are available to determine if the revised dosing regimen of 200 mg BID derazantinib either as monotherapy or in combination with atezolizumab is safe and tolerable.

The safety evaluation will comprise updating a three-parameter cumulative BLRM-EWOC design for the incidence of DLTs with monotherapy and combination therapy to strictly manage the risk of excessive toxicity (Neuenschwander 2008). For a derazantinib dose d , let π_d denote the probability of DLT at dose d . If n subjects are evaluated at dose d , then the number of subjects, y , experiencing a DLT is assumed to follow a binomial distribution:

$$y \mid \pi_d \sim \text{Binomial}(n, \pi_d)$$

The relationship between monotherapy and combination derazantinib doses, and DLT probabilities is modelled by the logistic curve;

$$\log(\pi_d/(1 - \pi_d)) = \log(\alpha_i) + \beta \log(d/d^*), \alpha_1, \alpha_2, \beta > 0$$

Doses are rescaled as d/d^* with reference dose $d^* = 600\text{mg/day}$. The model parameters α_1 , α_2 and β have the following interpretation:

- α_1 equals the odds of toxicity with monotherapy at the reference dose d^* .
- α_2 equals the odds of toxicity with combination therapy at the reference dose d^* .
- Doubling the dose results in an increase in odds of toxicity by a factor of 2β .

The model parameters $\log(\alpha_1)$, $\log(\alpha_2)$, $\log(\beta)$ are given a weakly informative multivariate normal prior distribution, following (Neuenschwander 2014), with prior means (-1.386, -1.386, -0.781), prior standard deviations (5.472, 5.472, 0.973), and prior correlations of 0. This prior distribution ensures wide confidence intervals for toxicity probabilities at each dose.

With an acceptable target toxicity range for a dose defined as a probability of toxicity of 10% to <25% and an overdosing range of $\geq 25\%$, the posterior probability of overdosing will be updated over time. Data resulting in a posterior probability of overdosing for a dose in excess of 25% will be determined as unacceptable. This ensures a safe recommended dose is chosen for subsequent testing of anti-tumor efficacy. This process also involves regular dose decision meetings to review the updated cumulative model results as well as safety in individual patients.

Safety and tolerability of both the monotherapy and the combination dose regimens, and restart of enrollment in Substudies 3 and 5 will be concluded by joint decisions taken by the IDMC, Investigators, and the Sponsor in reviewing the aggregate of DLT, AE and PK data from the first 10 patients each enrolled in Substudies 3 and 5.

Safety interim analyses of dose-limiting toxicities in substudies 3 and 5 will be undertaken entirely by Basilea Pharmaceutica International Ltd.

6.4.3. Physical and Ophthalmological Examinations

Physical examinations will be performed at pre-screening, screening, at each cycle, end of treatment and safety follow-up visits (28 days and 90 days after last dose, as applicable), and symptom-driven examinations will be done as needed. Ophthalmological examinations will be performed during screening, the first four cycles (i.e. Day 1 of Cycles 2–5) and the End of Treatment visit. Physical examination and ophthalmological results will be listed.

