This process also involves regular dose decision meetings to review the updated cumulative model results as well as safety in individual patients. Safety and tolerability of both the monotherapy and the combination dose regimens, and restart of enrollment in Substudy 3 and 5 will be concluded by joint decisions taken by the IDMC, Investigators, and the Sponsor in reviewing the aggregate of DLT, AE and PK data from the first 10 patients each enrolled in Substudies 3 and 5.

Analysis of secondary endpoints

DCR will be summarized in the same way as the primary endpoint.

DOR, PFS and OS analyses will be performed using Kaplan-Meier (KM) methods. The analysis will be performed on the mITT population.

Sensitivity analyses within **Substudy 4** will be performed according to the stratification factor composite score and its variables.

ASSESSMENTS

Pharmacokinetics

Sparse derazantinib PK sampling: In the Sparse derazantinib PK sampling population, derazantinib plasma concentrations at each nominal time-point will be summarized by substudy and cohort using descriptive statistics.

Rich derazantinib PK sampling: All SIA patients in Substudies 3 and 5 will undergo Rich derazantinib PK sampling for measurement of plasma concentrations of derazantinib and relevant PK parameters. In the Rich derazantinib PK sampling population, PK parameters will be determined by non-compartmental analysis. The following parameters will be determined: C_{max} , t_{max} , AUC_{0-12} , AUC_{0-24} , AUC_{last} . PK parameters from rich PK sampling will be summarized by Substudy and Cohort using descriptive statistics. Derazantinib plasma concentrations at each nominal time-point will be summarized by substudy and cohort using descriptive statistics.

In the atezolizumab PK population, atezolizumab and anti-drug antibodies (ADA) serum concentrations at each nominal time-point will be summarized by Substudy and Cohort using descriptive statistics.

Safety/tolerability

AE monitoring will be ongoing throughout the study and graded in severity according to the guidelines outlined in the National Cancer Institute CTCAE Version 5.0 (NCI CTCAE 5.0). AEs will be coded using the standard Medical Dictionary for Regulatory Activities (MedDRA), and grouped by System Organ Class and Preferred Term. Additional safety summaries will be provided for safety laboratory tests, vital signs, ECGs, physical examinations, ophthalmology examinations and ECOG PS.

Efficacy

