3.2.2 Secondary endpoints

- DCR, as measured by the proportion of patients with confirmed CR, PR or stable disease (SD)¹ by BICR
- DOR, as calculated from the first date of documented tumor response to disease progression by BICR
- Median PFS and PFS at 6 months, as determined by BICR and measured from time of first dose to time of objective tumor progression or death, and the proportion of patients alive and free of objective tumor progression 6 months after cohort assignment, respectively
- Median OS and OS at 6 months, as measured from time of first dose until time of death and the proportion of patients alive 6 months after cohort assignment, respectively
- Safety and tolerability of study drugs as measured by the frequency and severity of AEs, clinical laboratory parameters, vital signs, ECOG PS, physical examinations (including eye examinations), and ECG parameters over time, and graded by NCI CTCAE 5.0
- Derazantinib (and – if applicable –derazantinib metabolites) plasma concentrations, C_{max} , t_{max} , AUC_{0-12} , AUC_{0-24} , AUC_{last} assessed by measurements in blood samples during treatment as monotherapy (Substudy 5) or in combination (Substudy 3)
- Changes in HR-QoL and symptom response, measured by global, functional and symptom scores obtained from patient reported outcome instruments at baseline and over time (EORTC QLQ C30, FACT-BI, EQ-5D [5L] VAS), and Health Transition Index/G-SET.

¹ Evaluating target lesions, SD is defined as neither sufficient shrinkage to qualify for PR nor sufficient increase to qualify for Progressive Disease (PD, see following definition), taking as reference the smallest sum of diameters while on study. PD is defined as at least a 20% increase in the sum of diameters of target lesions, taking as reference the smallest sum on study (this includes the baseline sum if that is the smallest on study). In addition to the relative increase of 20%, the sum must also demonstrate an absolute increase of at least 5 mm. (Note: the appearance of one or more new lesions is also considered progression).

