7.2.6 Adverse events of special interest

The following are considered AEs of special interest (AESIs) for the purposes of this study, based on the known safety profiles of derazantinib and atezolizumab:

- Hyperphosphatemia/blood phosphorus increased
- Hyponatremia
- Stomatitis
- Nail disorder
- Ocular/eye disorder
- Liver function tests abnormal (compared to baseline)
- Serum creatinine increase or renal failure
- Hypertension / cardiac disorders
- QT prolongation
- Immune-related AEs (see Section 4.5.1)

All AESI must be recorded in the eCRF. In addition, immune-related AESIs, which are CTCAE grade ≥ 2 or are serious, and all other AESIs which are CTCAE grade > 2 or are serious, must be reported to the Sponsor within 24 hours using the SAE/AESI form.

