8.3.5.2 Other safety parameters

All AEs occurring during the study will be coded by standard MedDRA and grouped by System Organ Class and Preferred Term. Safety endpoints for AEs include the following: incidence of all TEAEs¹ and all serious AEs, AEs by severity, AEs by relationship to study drug, and discontinuation of patients from study therapy due to AEs and deaths.

Additional safety summaries will be provided for clinical laboratory tests, vital signs, ECGs, physical examinations, ophthalmology examinations, ECOG PS, and – if relevant – any drug exposure during pregnancy.

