6.8. Changes to Methods Planned in the Protocol

The planned Inverse Probability of Censoring Weighted (IPCW) modelling approach ([Rimawi 2012](#)) for crossover patients will not be undertaken due to low sample size of crossover patients.

7. Tables, Listings, And Figures

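### SAP 6.4.3 lists eye and physical examination results where the protocol promises summaries, so ocular toxicity is tabulated only through adverse event reports

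*SAP*

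**What the plan says.** The secondary safety endpoint in Protocol 3.2.2 includes "physical examinations (including eye examinations), and ECG parameters over time, and graded by NCI CTCAE 5.0". Protocol 8.3.5.2 then commits to the analysis: "Additional safety summaries will be provided for clinical laboratory tests, vital signs, ECGs, physical examinations, ophthalmology examinations, ECOG PS". The synopsis makes the same commitment: "Additional safety summaries will be provided for safety laboratory tests, vital signs, ECGs, physical examinations, ophthalmology examinations and ECOG PS".

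SAP 6.4.3 repeats the schedule: "Ophthalmological examinations will be performed during screening, the first four cycles (i.e. Day 1 of Cycles 2–5) and the End of Treatment visit". Its only output statement is "Physical examination and ophthalmological results will be listed". SAP 6.8 declares one change to the protocol's methods, which begins "The planned Inverse Probability of Censoring Weighted (IPCW) modelling approach" and concerns crossover patients. It does not mention examinations.

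On the adverse event side, Protocol 7.2.6 names "Ocular/eye disorder" among the events of special interest. SAP 6.4.1 reports the number and percentage of patients with any treatment-emergent event and with any event of special interest, and tabulates each type by system organ class and preferred term.

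**The concern.** Two parts of a stated secondary endpoint lose the analysis the protocol promised, and the SAP neither declares nor justifies the change.

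The eye examinations matter more. Protocol 1.5.1 and 7.1.1.2 class ocular disorders as an important potential risk of derazantinib, and the repeated examinations including OCT are among the measures for monitoring it. A listing gives no prespecified rate of new or worsened findings, no denominator of patients examined, and no change from baseline. An abnormal finding that the site did not judge to be an adverse event would appear in no table. Substudies 3 and 5 also use a higher daily dose than Substudy 1, and no examination measure would be tabulated for any of these groups.

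**Working it through.** The question is mainly textual, so the passages are set side by side.

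**1. Promise against delivery.** One sentence in Protocol 8.3.5.2 promises summaries for six routine data types. The SAP treats them as follows.

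| Data type | SAP section | Output specified |
|---|---|---|
| Laboratory tests | 6.4.6 | Summaries by visit, shift tables |
| Vital signs | 6.4.4 | Value and change from baseline by visit |
| ECG | 6.4.5 | Value, change, threshold categories, worst value |
| ECOG PS | 6.4.7 | Shift table |
| Physical examination | 6.4.3 | Listing |
| Ophthalmology | 6.4.3 | Listing |

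Four of the six are summarised and two are only listed. Vital signs and weight, which Protocol 5.3.2.1 places within the physical examination, are summarised in SAP 6.4.4, so for physical examination the gap is limited to the findings by body system. QT prolongation, which Protocol 1.5.2 rates as a non-important potential risk, receives threshold and worst-value tables. The scheduled examinations for an important potential risk receive none.

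**2. Was the change declared?** SAP 6.8 records only the dropped IPCW model. The move from summary to listing is undeclared.

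**3. What the adverse event tables capture.** Protocol 7.4.3.1.1 requires adverse events observed directly at an examination or other assessment to be recorded. Protocol Table 5 gives a grade and a dosing action even to an asymptomatic retinal finding, and dose changes must be captured. SAP 6.4.1 tabulates events leading to dose modification or interruption. A retinal finding handled under Table 5 is therefore likely to reach a table.

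**4. What they leave out.**
- Abnormal findings not recorded as adverse events. Protocol 5.3.2.1 and 5.3.2.4 say that clinically significant physical and ECG changes must be reported as adverse events. Section 5.3.2.3 on eye examinations has no such sentence, so only the general rule applies.
- The number examined at each visit as denominator. Adverse event percentages use all treated patients.
- Change from baseline by visit or at worst, which is what an endpoint measured over time calls for.
- Separation of Grade 1 from Grade 2 retinal findings. The SAP's adverse event tables single out only Grade 3 or higher.

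**5. Size.** The inputs are the schedule in Protocol Table 1 and the cohort sizes in Protocol 8.1.1 to 8.1.4.
- Scheduled eye examinations per patient: 1 (Screening) + 4 (Day 1 of Cycles 2 to 5) + 1 (End of Treatment) = 6.
- Patients if every active cohort fills: 74 + 36 + 50 + 50 + 26 = 236. Protocol 8.1 states 246; the difference does not affect this point.
- Patients if every cohort stops at Stage 1: 35 + 18 + 16 + 16 + 13 = 98, as Protocol 8.1 states.
- Ceiling on scheduled examinations: 6 × 236 = 1,416, or 6 × 98 = 588. Patients who stop before Cycle 5 contribute fewer.

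To show what a summary would report, take Substudy 5 with 26 patients, all assumed examined. One new retinal finding is 1/26 = 3.8%, exact 95% CI 0.1% to 19.6%. With none, the two-sided upper limit is 1 − 0.025^(1/26) = 13.2%. These limits follow from n = 26, not from the choice between table and listing.

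**The case against.** The strongest reply is that the safety signal is captured elsewhere. Ocular disorder is an event of special interest, all such events must be recorded, and the SAP tabulates them with percentages by preferred term. The endpoint wording also refers to CTCAE grading, so graded adverse event tables deliver part of it. This stands. A reader might infer from SAP 6.4.3 that no rate of ocular toxicity found at examination will be reported, or that this part of the endpoint goes wholly unanalysed. The documents support neither inference.

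It also stands that a reader could count 0 or 1 of 26 patients from a listing. That would be a hand count rather than a prespecified analysis.

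The protocol promises summaries without specifying their form. It does not promise shift tables for every eye component or an ocular comparison of the two derazantinib regimens. Protocol 5.3.2.3 leaves the components of the examination optional and asks for constant methods only within a patient. Complete, comparable data on acuity, tonometry, anterior segment and retina cannot be assumed, which argues for a modest table.

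Finally, SAP 7.2 places the table shells in a separate document that is not available here. They may already contain such a table, but the SAP text does not call for one. If they do, SAP 6.4.3 should be corrected to match.

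None of this answers the mismatch between the documents, its absence from SAP 6.8, or the lack of an examination-based summary.

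**Conclusion.** The point holds in a limited form. SAP 6.4.3 replaces promised summaries of physical and ophthalmological examinations with listings, and SAP 6.8 does not say so. Ocular toxicity is summarised only through the AE and AESI tables. There is no examination-based rate or change from baseline, and abnormal findings not recorded as adverse events are not tabulated.

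It affects up to six scheduled eye examinations per patient in between 98 and 236 patients, both counts being maxima for their scenario. How many findings would go untabulated cannot be estimated from the documents, because it depends on how sites record abnormal results. No primary result or dose decision is shown to change. The conclusion rests on the SAP text as written and assumes that the unseen shells follow it. The point is worth correcting before database lock because it concerns a secondary endpoint and an important potential risk, and the remedy is small.

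**What to change.** In SAP 6.4.3 add, by substudy and cohort:
- a summary of ophthalmological examinations giving n (%) of patients with a new or worsened finding relative to baseline, at each scheduled examination and at the worst post-baseline examination, with the number examined as denominator;
- coverage of at least retina/OCT, and visual acuity where collected, with an exact 95% CI for the proportion with any new retinal finding, whether or not it was recorded as an adverse event;
- a simple normal/abnormal shift table for physical examination, where the data allow.

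If the sponsor decides to drop any of these summaries, SAP 6.8 should declare and justify it.

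The cost is a few extra tables from examinations already scheduled, plus some coding of free-text findings. Some eye components may be incomplete because the protocol does not make them mandatory, and the number examined should be shown so that this is visible. No assessment, visit or clinical rule changes.

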6.4.4. Vital Signs

The actual value and change from baseline to each visit and at end of study will be descriptively summarized by visit/assessment for vital signs (i.e., systolic and diastolic blood pressure, heart rate, respiratory rate, temperature and body weight).

Height is measured at screening only. All vital sign data will be reported in a by-patient listing.

6.4.5. Electrocardiogram

The actual value and change from baseline to each visit and at end of study will be descriptively summarized by visit for ECG parameters (e.g., heart rate, RR interval, PR interval, QRS duration, QT interval, QTcF interval and QTcB interval). For all patients, a standard, triplicate, 12-lead ECG must be performed at all study visits using the pre-programmed device provided by the Sponsor. Summary tables will consider the mean of the triplicate measurements at each visit as the single reported value.

A categorical analysis of QTcF interval and QTcB interval correction will also be presented, based on the number and percentage of patients meeting or exceeding specific thresholds for absolute QTcF/QTcB interval prolongation and change from baseline in QTcF/QTcB interval. In this analysis, the mean of the triplicate measurements will not be used; instead, the maximum at each timepoint will be considered.

For absolute QTcF/QTcB interval prolongation, the number and percentage of patients within the following thresholds will be summarized at each visit. The worst (largest) value will also be summarized.

- Interval ≤ 450 ms
- Interval >450 ms and ≤ 480 ms
- Interval >480 ms and ≤ 500 ms
- Interval >500 ms

The change from baseline in QTcF/QTcB interval to the worst (largest) post-baseline observation and at each study visit will also be summarized, considering the following thresholds:

- Interval increased from baseline ≤ 30 ms
- Interval increased from baseline >30 ms and ≤ 60 ms
- Interval increased from baseline >60 ms

For the analysis of change from baseline, the mean of the triplicate measurements will be used for all visits. In the categorical analyses, the maximum of triplicate measurements will be used for post-baseline values.

These summary tables will be presented by timepoint, and for the maximum post baseline value.

All summary outputs for ECG will consider central ECG data.

All ECG data will be provided in a by-patient listing. Local ECG data will be listed only.

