5.3.2.3 Complete ophthalmological examination

A complete ophthalmological examination, including OCT, should be performed by an ophthalmologist at the Screening visit, for the first four cycles (i.e., Day 1 [± 7 d] of Cycles 2–5), and at the End of Treatment visit. Thereafter, a complete ophthalmological examination is to be repeated if clinically indicated (e.g., new ocular symptoms occur or vision is impaired).

The complete ophthalmological examination may include the following:

- visual acuity
- tonometry
- anterior segment evaluation
- retinal evaluation, including OCT

For the individual patient, the same methods of assessment should be used throughout the study. Patients who develop ocular symptoms or changes in visual acuity while on the

study should be referred to the ophthalmologist for a complete ophthalmological examination.

5.3.2.4 *Electrocardiogram (12-lead) triplicates*

For all patients, a standard, triplicate, 12-lead ECG must be performed at all study visits using the pre-programmed device provided by the Sponsor.

ECGs must always be recorded after at least 5 minutes rest and while the patient is in a sitting, semi-supine, or supine position. Measurements should be separated by ~1 minute and be taken within a 5-minute time window. The on-treatment ECGs (up to Cycle 4) should be performed as close as possible to the corresponding PK blood collection timepoint during those visits (see Section 5.3.4.1); if possible, ECG should be measured first, and then blood collected for PK within 5–10 minutes.

ECGs must be assessed by the Investigator or their designee for any abnormalities, including prolongation of QTcF. The ECG printouts are to be signed and dated by the Investigator or their designee. Further instruction and training on handling the device and transmitting data will be provided to the study centers prior to study initiation.

All ECGs are to be transmitted to a central ECG laboratory for evaluation, including QTcF assessment. Any clinically-significant ECG change from baseline that occurs after first study drug administration must be reported as an AE (see Section 7.4.3).

5.3.2.5 *Clinical safety laboratory blood tests*

Blood samples for clinical safety laboratory testing should be performed locally at all study visits. For C1D1, clinical safety laboratory testing must be performed within 72 hours prior to study drug administration.

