In alignment with interventions to ensure patient safety and for the purpose of this protocol, hyperphosphatemia is defined as:

- Grade 1: > ULN to < 7.0 mg/dL (< 2.26 mmol/L)
- Grade 2: Non-invasive intervention required (e.g., withhold drug or modify dose) or between 7.0 – 9.0 mg/dL (2.26 – 2.90 mmol/L)
- Grade 3: Severe or medically significant, but not immediately life threatening or > 9.0 – 10.0 mg/dL (> 2.90 – 3.23 mmol/L)
- Grade 4: Life-threatening consequences, urgent intervention indicated e.g., dialysis or > 10.0 mg/dL (> 3.23 mmol/L)

Patients who present with serum phosphate ≥ 7.0 mg/dL, adding an oral phosphate binding/reducing agent¹ until serum phosphate level returns to < 5.6 mg/dL should be considered, and patients should be instructed to adhere to a low-phosphate diet.

6.1.1.5.2 *Management of retinal adverse events*

A complete ophthalmological examination (see Section 5.3.2.3) should be performed by an ophthalmologist at the Screening visit, for the first four cycles (i.e., Day 1 of Cycles 2–5), and at the End of Treatment visit. Further complete ophthalmological examinations only need to be performed if clinically indicated. [Table 5](#) provides specific guidance for the management of dose delays/reductions in the case of retinal adverse events possibly related to derazantinib.

6.1.1.5.3 *Management of QTc prolongation or other significant ECG abnormalities*

If significant QTc prolongation and/or significant ventricular arrhythmia is observed, i.e., a prolonged QTcF interval ≥ 501 ms on at least two separate ECGs (mean values from triplicate ECGs, consistent with a CTCAE grade 3 event), the patient must be monitored by the Investigator and hourly (triplicate) 12-lead ECG obtained until the mean QTcF has returned to ≤ 450 msec for males or to ≤ 460 msec for females. The clinical context and possible factors contributing to QTc prolongations such as electrolyte abnormalities (potassium, calcium or magnesium), concomitant medications, or other clinical factors such as cardiac ischemia must be carefully assessed, and any findings documented in the eCRF. The decision to continue treatment with derazantinib should be reviewed and supported by a cardiologist.

¹ Either calcium-containing (e.g., calcium carbonate and calcium acetate) or non-calcium-containing (e.g., sevelamer) phosphate binders, and/or phosphaturic agents, depending on serum calcium levels and in accordance with institutional guidelines, recommendations, and schedules.

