6.1. Statistical and Analytical Issues

6.1.1. Statistical Methods

Tabulations will be produced for appropriate demographic, baseline, safety and efficacy parameters. Continuous variables will be summarized by reporting the number of observations, mean, standard deviation, median, first quartile (Q1), third quartile (Q3), minimum, and maximum. Categorical variables will be summarized using frequency tables showing the number and percentage of patients within a particular category, where the denominator is the number of patients within the category at applicable time point (unless otherwise specified). Time-to-event data will be summarized using the Kaplan-Meier method.

By-patient data listings will be produced for data collected through the study (e.g., CRF, lab). All data listings that contain an evaluation date will contain a relative study day (Study Day). Pre-treatment and on-treatment study days are numbered relative to the day of the first dose of study medication, which is designated as Day 1. The preceding day is Day -1, the day before that is Day -2, etc. Baseline will be defined as the last evaluable/non-missing observation/assessment prior to the first dose of study drug on Cycle 1, Day 1.

Statistical analyses will be carried out by using SAS Version 9.4 or higher. Any deviations from the planned analysis as described in the SAP will be justified and recorded in the clinical study report.

Adverse events will be graded by the Investigator based on the National Cancer Institute (NCI) Common Terminology Criteria for Adverse Events (CTCAE), Version 5.0, and will be coded for summarization using the Medical Dictionary for Regulatory Activities (MedDRA® Version 22.0 or later). Concomitant medications will be coded using the World Health Organization (WHO) Drug Dictionary (March 2019 version or later).

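### SAP 6.4.5 appears to compare the maximum of three post-baseline QTc tracings with a mean baseline in the change categories, which inflates the >30 ms counts

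*SAP*

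**What the plan says.** SAP 6.4.5 makes the triplicate mean the default: "Summary tables will consider the mean of the triplicate measurements at each visit as the single reported value". It then introduces categorical tables of absolute QTcF/QTcB and of change from baseline, and says of them: "In this analysis, the mean of the triplicate measurements will not be used; instead, the maximum at each timepoint will be considered". The change categories are cut at 30 and 60 ms and are taken both by visit and at the worst value: "The change from baseline in QTcF/QTcB interval to the worst (largest) post-baseline observation and at each study visit will also be summarized".

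After those cut-points come two consecutive sentences. The first is "For the analysis of change from baseline, the mean of the triplicate measurements will be used for all visits". The second is "In the categorical analyses, the maximum of triplicate measurements will be used for post-baseline values".

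No sentence says which summary of the baseline triplicate enters the categorical change. SAP 6.1.1 gives only the general rule: "Baseline will be defined as the last evaluable/non-missing observation/assessment prior to the first dose of study drug on Cycle 1, Day 1". Protocol 5.3.2.4 makes the three tracings replicates of one timepoint: "Measurements should be separated by ~1 minute and be taken within a 5-minute time window".

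**The concern.** The only sentence that separates baseline from post-baseline limits the maximum to post-baseline values. With the mean as the section's default, the change becomes a maximum of three minus a mean of three. The maximum of several noisy readings lies above their mean on average, so the difference is positive even if the drug does nothing.

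QT prolongation is an adverse event of special interest in Protocol 7.2.6, and the >30 ms count is a table a reader will look at. Every arm in the study receives derazantinib, so nothing inside the trial would show how much of the count is measurement noise. The wording also leaves a programmer to choose between derivations that give different tables.

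**Working it through.** **Readings of the text.** Three derivations can be defended.

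- Maximum minus mean: the sentence naming post-baseline values, combined with the default mean. This is the most specific reading.
- Maximum minus maximum: if each timepoint is taken to include baseline.
- Mean minus mean: if the sentence on change from baseline, which follows directly after the change cut-points, is taken to govern them.

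**Inputs.** The documents give the triplicate design and the 30 and 60 ms cut-points. They give no variance figures and no QTc result, so there is no figure in the plan to reproduce. Three inputs are assumptions:

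- within-triplicate SD (s_w) of 4 to 12 ms, with 5 to 10 ms as the main range;
- visit-to-visit SD of the underlying level (s_b) of 0 to 10 ms, with 8 to 10 ms as the main range;
- eight post-baseline timepoints. This fits Protocol 5.2.2: C1D1 post-dose, C1D15 pre- and post-dose, C2D1, C3D1 pre- and post-dose, C4D1 and End of Treatment. Patients who stay longer, and the safety interim patients, have more.

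**Shift at one visit.** For three independent normal readings, E[maximum] − mean = 3/(2√π) × s_w = 0.846 × s_w.

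- s_w = 5 ms: 0.846 × 5 = 4.2 ms
- s_w = 8 ms: 0.846 × 8 = 6.8 ms
- s_w = 10 ms: 0.846 × 10 = 8.5 ms

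A single-tracing baseline gives the same expected shift. Using the same summary on both sides gives zero.

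**Patients crossing 30 ms with no true change.** Simulation of 400,000 patients with independent normal errors; entries are percentages of patients.

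| s_w / s_b (ms) | One visit: mean−mean | One visit: max−mean | One visit: max−max | Worst of 8: mean−mean | Worst of 8: max−mean | Worst of 8: max−max |
|---|---|---|---|---|---|---|
| 4 / 6 | 0.04 | 0.2 | 0.06 | 0.4 | 1.5 | 0.6 |
| 8 / 6 | 0.3 | 2.2 | 0.6 | 1.7 | 11.9 | 4.0 |
| 8 / 10 | 2.7 | 7.5 | 3.5 | 13.5 | 30.7 | 16.5 |
| 10 / 10 | 3.4 | 10.3 | 4.5 | 15.7 | 39.2 | 20.3 |

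Check of one cell (8 / 6, one visit, mean minus mean): the variance of the change is 2 × 6² + 2 × 8²/3 = 72 + 42.7 = 114.7, so the SD is 10.7 ms. Then 30/10.7 = 2.80, and the upper normal tail is about 0.25%, against 0.26% simulated before rounding.

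Over the main range (s_w 5 to 10, s_b 8 to 10), the worst-of-eight figures run from 3.8% to about 16% for mean minus mean and from 9.7% to about 39% for maximum minus mean. They are about 5 to 21% for maximum minus maximum.

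**Patients crossing 60 ms.** Under maximum minus mean the figure never exceeds 0.33% at one visit or 2.2% for the worst of eight. Both occur at the extreme corner of the grid (12 / 10). In the main range the worst-of-eight figure stays below 1%.

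**The case against.** The strongest reply is that a mean baseline is inferred. The phrase about each timepoint can include baseline, and the mean rule for change sits directly under the change cut-points. On either of those readings the single-visit shift disappears. This stands as to certainty. The sentence naming post-baseline values still points most directly to the mismatch, and a rule with three workable readings needs settling in any case.

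It is also fair that the tables are descriptive, with no test or decision rule attached. A maximum may be deliberate caution, though the SAP does not say so. The continuous change analysis uses means throughout and is unaffected. The Protocol 1.5.2 footnote on QT classes the risk as non-important. These points limit the importance of the finding. They do not justify different summaries on the two sides of a subtraction.

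A reader might go further and infer that the >60 ms and >500 ms counts are inflated in the same way. The documents do not support that. The >60 ms band barely moves in the calculation. The >500 ms band is an absolute value with no baseline subtracted, so reporting its maximum is a choice about conservative display.

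A reader might also infer that the maximum is what stops these tables matching the protocol's QTcF rules, which use "mean values from triplicate ECGs, consistent with a CTCAE grade 3 event" in Protocol 6.1.1.5.3. That rule also requires at least two separate ECGs, and the eligibility limits are sex-specific. The SAP bands would not reproduce either rule even with means.

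**Conclusion.** The point holds as a minor one about the change-from-baseline categories. The direction is certain on the maximum-minus-mean reading: any replicate variability produces a positive shift of 0.846 s_w. Its size is conditional on SDs and a timepoint count that the documents do not supply. At s_w = 4 ms with no visit-to-visit variation, no simulated patient crossed 30 ms, although the average shift remained.

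The gap between the two rules must not be confused with the total. Taking the worst value over visits produces noise-driven counts under every rule, and the 4 to 16% seen with means on both sides is that residual. Only the excess over it is due to the unmatched baseline. A reader might infer that matching the summaries would clear noise from the table, and it would not.

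**What to change.** State in SAP 6.4.5 that, for the change-from-baseline categories, both the baseline and every post-baseline value are triplicate means, and that the worst post-baseline value is the largest of those means. This follows the SAP's own continuous change analysis and removes the ambiguity between the sentences. Restrict the maximum rule explicitly to the absolute-value categories, if it is wanted there, and label those tables as single-tracing maxima. Individual tracings remain in the by-patient ECG listing already planned.

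The cost is one derivation rule and a table footnote. No data collection changes. The downside is that the change categories lose their worst-single-tracing view and the >30 ms counts become smaller, so the change should be made and dated before the ECG tables are produced.
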